10.6 Dexamethasone Toxicity

Fluid retention is common with Dexamethasone in patients with amyloidosis. Optimisation and close monitoring of fluid balance including alteration of diuretic therapy according to daily weights should be considered as the first step. For fluid retention, switching to an alternative corticosteroid, e.g. methylprednisolone, is unlikely to be of major benefit as the mineralocorticoid action is greater for most other corticosteroids than for Dexamethasone at comparable doses.

If a patient experiences grade 3 or 4 toxicity directly attributable to Dexamethasone a dose reduction should be considered. Dose adjustments should be at the discretion of the treating physicians in view of appreciable variability in the manifestation of such side effects. Dexamethasone should be reduced in 4mg steps.

Please see the SPC for expected toxicities.

10.7 Thalidomide Toxicity

Cases of viral reactivation, some serious, have been reported following treatment with thalidomide, particularly in patients previous infected with the varicella zoster virus or hepatitis B virus (HBV). Some of the cases of reactivation resulted in disseminated herpes zoster, requiring antiviral treatment and thalidomide treatment

interruption. Some cases of HBV reactivation progressed to acute hepatic failure and resulted in thalidomide treatment discontinuation.

Hepatitis B virus status should be established before initiating treatment with thalidomide. For patients who test positive for HBV, consultation with a physician with expertise in the treatment of hepatitis B is recommended. Previously infected patients should be closely monitored for signs and symptoms of viral reactivation, including active HBV infection, throughout therapy. Patients who test positive for HBV will not be eligible for the CATALYST trial.

Cases of pulmonary hypertension, some fatal, have been reported following treatment with thalidomide.

If a patient experiences grade 3 or 4 toxicity directly attributable to Thalidomide a dose reduction should be considered. Dose adjustments should be at the discretion of the treating physicians in view of appreciable variability in the manifestation of such side effects. Patients receiving 100mg should be reduced to 50mg. Patients receiving 50mg should have their dose discontinued.

Please see the SPC for expected toxicities.

10.8 Increased Creatinine or Decreased CrCl

Carfilzomib should be withheld for CrCl < 15 mL/min, and re-commenced as detailed in Table 5. Patients whose renal function fails to recover may re-commence therapy after discussion with the CI.

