Grade 2 treatment emergent neuropathy with pain or Grade 3 neuropathy	Continue to dose. If neuropathy persists for more than two weeks hold Carfilzomib until resolved to \leq Gr 2 without pain. Then restart at 1 dose decrement
\geq Grade 3 elevation in LFTs (AST, ALT, or total bilirubin)	Withhold dose. Resume at 1 dose decrement when toxicity has resolved to baseline.
Grade 4 neuropathy	Discontinue (refer to section 14)
Renal Dysfunction Serum creatinine equal to or greater than 2 x baseline, or CrCl $<$ 15mL/min (or CrCl decreases to \leq 50% of baseline) or need for dialysis.	Withhold dose and continue monitoring renal function (serum creatinine or serum creatinine clearance). If attributable to Carfilzomib, resume when renal function has recovered to within 25% of baseline. Start at 1 dose level reduction. If not attributable to Carfilzomib, dosing may be resumed at the discretion of the physician. If tolerated, the reduced dose may be escalated to the previous dose at the discretion of the physician. For patients on dialysis during Carfilzomib, the dose is to be administered after the dialysis procedure.
Congestive heart failure and other cardiopulmonary disorders.	See section 10.10. Any participant with marked worsening of symptoms of congestive heart failure, whether or not drug related, must have the dose withheld until resolution or return to baseline, after which treatment may continue at a reduced dose, or the subject may be permanently discontinued
Other non-haematologic toxicity assessed as Carfilzomib-related \geq Grade 3	Withhold dose until toxicity resolves to \leq Grade 2 or baseline. Restart at 1 dose decrement. If tolerated, the reduced dose may be escalated to the previous dose at the discretion of the physician.
PRES (posterior reversible encephalopathy syndrome with symptoms including headaches, altered mental status, seizures, visual loss, and hypertension).	If PRES suspected, withhold Carfilzomib. Consider evaluation with neuroradiological imaging for onset of visual or neurological symptoms suggestive of PRES. If PRES diagnosis is excluded, Carfilzomib administration may resume if clinically appropriate.

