10.9 Infections

Participants with active or suspected infections of grade III or greater should have treatment withheld until infection has resolved and anti-infective treatment has been completed. After the infection has resolved and anti-infective treatment has been completed, treatment may continue at the original dose. If there is no resolution of toxicity to ≤ Grade 1 or baseline after 3 weeks, the participant will be discontinued from treatment (see section 14).

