10.12 Carfilzomib Safety Considerations

Based upon the experience in the Phase 1 and 2 clinical studies with Carfilzomib, the following observations are noted:

- A “first dose effect” has been seen, which is notable for fever, chills, rigors, and/or dyspnoea occurring during the evening following the first day of infusion and an increase in creatinine on Day 2, which may be the clinical sequelae of rapid tumour lysis and/or cytokine release.
- Should a “first dose” effect occur at any point during Cycle 1 or 2, treatment with high dose glucocorticoids (e.g. methylprednisolone 50–100 mg) is recommended. In addition, intravenous fluids, vasopressors, oxygen, bronchodilators, and acetaminophen should be available for immediate use and instituted, as medically indicated.
- Dexamethasone will be administered prior to all Carfilzomib doses to prevent infusion reactions. See section 9.3.3 for more details.
- Acyclovir or similar should be given to all participants with a history of herpes simplex or zoster, per institutional prophylaxis guidelines, unless contraindicated.
- CrCl changes are mostly transient, reversible, and non-cumulative. All participants should be well hydrated. Clinically significant electrolyte abnormalities should be corrected prior to dosing with Carfilzomib. Renal function must be monitored closely during treatment with Carfilzomib. Serum chemistry values, including creatinine, must be obtained and reviewed prior to each dose of Carfilzomib during Cycles 1 and 2. Carfilzomib must be withheld for participants with a CrCl $<$ 15 mL/min at any time during study participation.
- Participants with active or suspected infection of any kind that required systemic treatment should not be dosed with Carfilzomib until the infection has resolved.
- Cases of gastrointestinal, pulmonary, and intracranial haemorrhage have been reported in patients treated with Carfilzomib, and are often associated with thrombocytopenia. Thrombocytopenia has been transient, with platelet nadirs seen between Day 8 and Day 15 of dosing, and typically resolves to baseline by the start of the next cycle. Platelet counts should be monitored frequently during treatment with Carfilzomib. For platelet counts $\leq 10 \times 10^9/L$ with evidence of bleeding, Carfilzomib dosing must be withheld. If platelet counts do not recover, the dose of Carfilzomib may be reduced or held according to the Dose Reductions / Adjustments rules outlined in Section 10.4.

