- Thromboembolic events, including deep vein thrombosis and pulmonary embolisms, have been reported in patients taking Carfilzomib, and some events have had fatal outcomes. Thromboprophylaxis, as outlined in section 9.2, should be administered to all participants receiving Carfilzomib.
- Participants should have anaemia corrected in accordance with the Institutional guidelines.
- Carfilzomib treatment can cause nausea, vomiting, diarrhoea, or constipation sometimes requiring the use of antiemetics or antidiarrhoeals. Fluid and electrolyte replacement should be administered to prevent dehydration.
- Posterior reversible encephalopathy syndrome (PRES), formerly termed reversible posterior leukoencephalopathy syndrome (RPLS), is a rare neurological disorder, which can present with seizure, headache, lethargy, confusion, blindness, altered consciousness, and other visual and neurological disturbances, along with hypertension. The diagnosis is confirmed by neuro-radiological imaging. If diagnosed early and treated, the symptoms of PRES may be reversed. Cases of PRES have been reported in subjects receiving Carfilzomib. Discontinue Carfilzomib if PRES is suspected. Refer to the study protocol for further instructions regarding dose modifications. The safety of reinitiating Carfilzomib therapy in subjects previously experiencing PRES is not known.
- Cases of thrombocytopenic thrombotic purpura/hemolytic uremic syndrome (TTP/HUS) including those with fatal outcome have been reported in subjects who received Carfilzomib. Monitor for signs and symptoms of TTP/HUS. If the diagnosis is suspected, stop Carfilzomib and manage per standard of care including plasma exchange as clinically appropriate. If the diagnosis of TTP/HUS is excluded, Carfilzomib can be restarted.
- Hypertensive crises have been infrequently reported in subjects treated with Carfilzomib. Hypertensive crises can present as hypertensive urgency or as a hypertensive emergency. Hypertensive urgency is defined as sustained or persistent systolic blood pressure 180mmHg or higher or diastolic blood pressure 110mmHg or higher, with no associated organ damage. A hypertensive emergency occurs when blood

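### Protocol sections 10.2, 10.8, 10.9, 10.12 and Table 5 conflict on holding and restarting carfilzomib for infection and for creatinine clearance that stays below 15 mL/min, and two different places are named as governing

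*Protocol*

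**What the plan says.** **Infection.** Protocol 10.12: "Participants with active or suspected infection of any kind that required systemic treatment should not be dosed with Carfilzomib until the infection has resolved". Protocol 10.9: "Participants with active or suspected infections of grade III or greater should have treatment withheld until infection has resolved"; it adds a second condition, that the anti-infective course is finished. The infection row of Table 5 (section 10.5) covers grades 3 and 4 and sets the same two conditions.

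**Renal function.** Protocol 10.8: "Carfilzomib should be withheld for CrCl < 15 mL/min, and re-commenced as detailed in Table 5". Its next sentence: "Patients whose renal function fails to recover may re-commence therapy after discussion with the CI". Protocol 10.12: "Carfilzomib must be withheld for participants with a CrCl" below 15 mL/min, whenever in the study this occurs, with no exception. Table 5 requires recovery to within 25% of baseline if the event is attributable to carfilzomib. If it is not, restart is left to the physician and no CrCl floor is given. The same row makes a requirement for dialysis a reason to withhold, and ends: "For patients on dialysis during Carfilzomib, the dose is to be administered after the dialysis procedure". Section 10.2 (subsequent cycles) takes the patient off therapy if an adverse event is unresolved at 14 days.

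**PRES.** Protocol 10.12: "Discontinue Carfilzomib if PRES is suspected". Table 5: "If PRES suspected, withhold Carfilzomib", with resumption possible once the diagnosis is excluded.

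**Which section governs.** Section 9.3.3 names 10.12 as the place that sets out management of decreased creatinine clearance and infection, and sends toxicities it does not list to 10.4 and 10.5. The last paragraph of 10.2 sends all toxicities, except neuropathic pain and peripheral sensory neuropathy, to Tables 3 and 5.

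The SAP has no holding rules. It repeats the DLT definition (2.3.1) and the delay, compliance and relative dose intensity definitions (2.3.2).

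**The concern.** These are operative instructions in the current text, to be applied at 15 sites. If two sections give different answers for the same patient, sites can differ in whether they dose while each follows the protocol. That is first a safety matter, in a population where amyloid kidney involvement is one of the listed organ involvements. The infection conflict can arise as early as the first dose, because exclusion criterion 16 admits a patient with systemic infection who is on specific anti-infective therapy.

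It also reaches the data. Holds and stops feed the endpoints on dose delays, withdrawal from treatment and relative dose intensity. The compliance endpoint requires treatment to have been given according to the protocol, which has no single meaning where the protocol gives two rules. A long enough hold in cycle 1 can, under conditions, count as a DLT, and in a 3+3 cohort a single DLT changes the escalation decision.

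**Working it through.** There is no sample size, power or event figure to reproduce. The check takes test patients through each section and asks whether carfilzomib may be given.

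| Situation | 10.12 | 10.8 or 10.9 | Table 5 | 10.2 |
|---|---|---|---|---|
| A. Grade 1–2 infection on systemic treatment | Hold | Trigger not met (10.9) | Trigger not met | Trigger not met (grade 3/4) |
| B. Grade 3 infection, resolved, anti-infective course unfinished | Hold condition ended | Still held (10.9) | Still held | Unfinished course not addressed |
| C. CrCl still below 15, not attributable to carfilzomib | Hold | Restart possible once discussed with the Chief Investigator (10.8) | Restart left to physician | Off therapy if unresolved at 14 days |
| D. CrCl still below 15, attributable | Hold | Restart possible once discussed with the Chief Investigator (10.8) | No restart until within 25% of baseline | Off therapy if unresolved at 14 days |
| E. PRES suspected, then excluded | Discontinue; no restart clause in the bullet | – | May resume | – |

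**Infection (A, B).** The sections differ in both trigger and end of hold, and in opposite directions: 10.12 is the wider rule in A and the shorter one in B. Neither rule contains the other.

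**Renal (C, D).** All three renal texts agree on the trigger. The disagreement is about what follows if CrCl does not rise above it. Two calculations mark its limits, treating eGFR and CrCl as similar, which is an assumption.

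- Recovery above 15 but short of the Table 5 target. Take, for illustration, a baseline of 40, a fall to 14 and a recovery to 22 mL/min. The target is 0.75 × 40 = 30. Since 22 < 30, renal function has not recovered in Table 5's sense and 10.8 applies; since 22 > 15, 10.12 does not bar dosing. Sections 10.8 and 10.12 do not clash here.
- Lowest baseline allowed at entry. eGFR below 20 mL/min is excluded. At a baseline of 20 the Table 5 target is 0.75 × 20 = 15, so the attributable route does not by itself lead to dosing below 15. The clash with 10.12 comes from 10.8's non-recovery sentence and from Table 5's non-attributable route.

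**Dialysis.** Table 5 withholds when dialysis is needed and then gives dose timing for a patient on dialysis, without saying when such a patient may restart. This is a gap rather than two opposite orders.

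**Precedence.** For creatinine clearance and infection, 9.3.3 leads to 10.12 and 10.2 leads to Table 5. No text says which prevails. For PRES both routes lead to Table 5: 9.3.3 through 10.5, and 10.2 directly.

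**Link to DLTs (Protocol 8.1.4, SAP 2.3.1).** Criterion 4 covers a delay of more than 8 days within cycle 1, or of more than 14 days in starting cycle 2. It counts only if the event is related to trial drug, the delay is due to significant toxicity or a tolerability issue, and no other DLT criterion explains it. Only DLTs attributed to the registered dose enter the MTD decision.

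**The case against.** The strongest replies are these.

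1. *No text orders dosing at grade 2.* Section 10.9 and Table 5 say what to do from grade 3; neither says that lower grades must be dosed, so a site holding under 10.12 breaches neither. That is correct, but a site that doses under 10.9 and Table 5, to which 10.2 sends it, does breach 10.12. The end-of-hold difference in B also remains.
2. *The renal rules share a trigger, and 10.8 can be read as a specific exception to 10.2's general 14-day rule.* The shared trigger is conceded, and the conflict is confined to CrCl that stays below 15. The exception reading is possible but nowhere stated, and it does not reconcile 10.8 with 10.12, which allows no exception.
3. *PRES is already handled.* Both texts stop dosing on suspicion, the 10.12 bullet refers onward for dose modifications, and 9.3.3 leads to Table 5. This mostly stands. What is left is terminology: Table 5 uses discontinuation elsewhere as an action distinct from withholding, and the neighbouring 10.12 bullet on TTP/HUS has a restart clause that the PRES bullet lacks.
4. *The Safety Review Committee attributes each DLT and judges evaluability case by case.* This limits the effect on the MTD. It does not remove differences in dosing between sites or in the delay-based endpoints.

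A reader might also infer that a loss of about 5 mL/min from the entry limit (20 − 15 = 5) puts a patient into the conflict. It reaches only the trigger, where the sections agree. Nor do the documents support reading every toxicity hold over 8 days in cycle 1 as a DLT, given the conditions in criterion 4.

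**Conclusion.** The point holds for infection and for renal function, and the contradictory precedence statements mean the protocol does not resolve either. For infection the sections differ at grades 1–2 on systemic treatment, and at grade 3 once resolved with treatment unfinished. For renal function they differ only while CrCl remains below 15 mL/min. The dialysis wording is an omission and PRES a minor mismatch; a reader might count PRES as a third full contradiction, but both texts stop dosing on suspicion and the protocol's own routing leads to Table 5.

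The size of the effect cannot be stated. The documents give no expected frequency of these events and no basis for estimating how sites would divide between the rules. The conclusion rests on the literal text; only the two boundary calculations assume that eGFR and CrCl are comparable. A reader might infer that Table 5 ought to prevail. The documents do not establish that, and choosing it would itself select a clinical rule.

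**What to change.** Reconcile sections 9.3.3, 10.2 (the 14-day rule and the closing reference to Tables 3 and 5), 10.8, 10.9, 10.12 and the infection, renal and PRES rows of Table 5, so that one rule applies to each of:

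- infection below grade 3 on systemic treatment;
- the end of the hold when an infection has resolved but treatment is unfinished;
- CrCl that stays below 15 mL/min, including how the 14-day rule applies;
- whether and when a patient on dialysis may restart;
- PRES suspected and then excluded (alignment of wording).

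State which section takes precedence and have the others cross-refer to it instead of restating a rule. Which rule and which section govern is for the sponsor and the clinical team. The cost is a protocol wording amendment and a note to sites; no extra patients or procedures are needed.

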10.9 Infections

Participants with active or suspected infections of grade III or greater should have treatment withheld until infection has resolved and anti-infective treatment has been completed. After the infection has resolved and anti-infective treatment has been completed, treatment may continue at the original dose. If there is no resolution of toxicity to ≤ Grade 1 or baseline after 3 weeks, the participant will be discontinued from treatment (see section 14).

10.10 Congestive Heart Failure

New or worsening cardiac failure, myocardial ischaemia, and myocardial infarction have occurred following Carfilzomib administration, with the risk of cardiac failure increased in elderly subjects (≥ 75 years). Worsening of congestive cardiac failure and other cardiopulmonary disorders including pulmonary oedema, and decreased ejection fraction will need careful assessment in relation to baseline cardiac status for the patient since many amyloid patients will have stable heart failure prior to trial entry.

If left ventricular ejection fraction (LVEF) decreases occur (for resting LVEF < 40% or reduction of LVEF to <55% if the drop is greater than 20% from baseline), withhold Carfilzomib until LVEF returns to > 40% or, if held due to a drop, < 55% within 15% of baseline. Resume at a 1-dose decrement.

Any participant with marked worsening of symptoms of congestive heart failure, whether or not drug related, must have the dose withheld until resolution or return to baseline, after which treatment may continue at a reduced dose, or the subject may be permanently discontinued. If no resolution after 2 weeks, participant will be permanently discontinued.

Any participant with significant worsening symptoms of CHF which has not resolved with an increase in diuretics prior to the next dose, or any other acute cardiac event, whether or not drug related, must have treatment withheld until resolution. After the event has resolved, treatment may continue at the previous dose, or one dose level lower than the previous dose. If there is no resolution of worsening of CHF after 2 weeks or further worsening after the next dose, the participant will be discontinued from treatment.

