8.1 Treatment Schedule Summary

8.1.1 KTD Regimen

All treatment will take place at the patient's RHC/Site.

If there is a ≥ 21 day delay in starting trial treatment after completion of eligibility confirmation form at the RHC, a second eligibility confirmation form must be completed. Patients must start treatment within 6 weeks of completion of the initial eligibility confirmation form.

Treatment will be as below with three regimes based on gradually increased dose and addition of Dexamethasone based on clonal response at end of each cycle.

KTD protocol – dose escalation phase

Carfilzomib

Days 1, 8,15

30 minute IV infusions of Carfilzomib at a dose according to table 1 below. A maximum of 6 cycles will be administered. All patients will be recommended oral hydration with 250 ml of fluids 2 hours before and one hour after the infusion at day 1. Oral hydration with 250 ml of fluids 2 hours before the infusion is recommended from day 8 onwards. Post infusion hydration is optional and at the discretion of the treating physician for patients at risk of tumour lysis syndrome and/or dehydration. Patients should be monitored closely for fluid overload.

All patients will receive Carfilzomib at 20mg/m² on day 1 of cycle 1 and then at the allocated dose level on day 8 and day 15 of cycle one, and during all subsequent cycles.

Thalidomide

1-28

50mg Thalidomide, oral preparation (potentially increasing to 100mg if well Days 1-28 tolerated - to be discussed with the Chief Investigator before increasing dose)

Dexamethasone

Days 1, 8,15

20mg Dexamethasone, oral preparation. This should be taken prior to all Carfilzomib doses.

Table 1: Dose Levels

Dose level	Carfilzomib IV (mg/m ²) (Days 1, 8 & 15)	Thalidomide (mg) (Days 1-28)	Dexamethasone (mg) (Days 1, 8 & 15)
-1	27	50	20
0	36	50	20
1	45	50	20
2	56	50	20

A minimum of 15 days must have elapsed between the start of treatment of the first patient in each cohort and subsequent patients.

KTD protocol – dose expansion phase

The dose escalation phase will then be extended once maximum tolerated dose (MTD) and the Recommended Dose (RD) has been established. All patients will then receive Carfilzomib-Thalidomide -Dexamethasone as follows (repeated every 28 days)

Carfilzomib Carfilzomib intravenous infusion at Recommended Dose (RD) .
Days 1, 8,15 A maximum of 6 cycles will be administered.

All patients will receive Carfilzomib at 20mg/m² on day 1 of cycle 1 and then RD from day 8 onwards

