10.2 Subsequent cycles (all patients)

In summary treatment should be delayed for any patient experiencing:

- Grade 4 thrombocytopenia with active bleeding
Grade 4 anaemia and Grade 4 thrombocytopenia (without active bleeding) do not require the Carfilzomib dose to be withheld. Participants should receive supportive measures in accordance with institutional guidelines.
- Grade 4 neutropenia or neutropenic fever
- Grade 3/4 non-haematological toxicity

Treatment should continue to be withheld until the neutrophil count and platelet count return to $\geq 0.75 \times 10^9/L$ and $\geq 25 \times 10^9/L$, respectively (during a cycle). Drug-induced non-haematological toxicities have to have reached baseline, or become Grade ≤ 1 prior to re-treatment. Treatment may be delayed up to 8 days to allow sufficient time for recovery from toxicities. Please check table 3 and table 5 for dose reduction guidelines.

If the haematological or non-haematological AE has not resolved within 14 days the patient must discontinue from therapy, if the haematological or non-haematological toxicities have resolved within 14 days, the patient may have their therapy re-instituted at the next lowest dose level. Please check table 3 and table 5 for dose reduction guidelines.

A dose delay of up to 14 days (up to 3 weeks for infection treatment) is permitted at the beginning of a cycle to allow resolution of toxicity. If there is no resolution of toxicity as stated above after 2 weeks of withholding treatment (3 weeks for infection treatment), the participant will be discontinued from treatment. Withholding treatment for more than 2 weeks for other reasons, eg elective surgery such as vertebroplasty, may be permitted after discussion with the CI.

No more than three dose reductions or delays in two consecutive cycles will be permitted in an individual participant on study. If toxicity continues or recurs after three dose reductions or delays, the participant should be discontinued from treatment.

If a patient vomits after taking a dose of an oral agent, no repeat dose should be taken and patient will continue as per schedule but the clinical team should consider prophylactic antiemetics.

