10.5 Dose Reductions for Non-Haematologic Toxicities

Carfilzomib should be withheld for events \geq Grade 3 until resolved to \leq Grade 1 or return to baseline.

After resolution of the event to \leq Grade 1 or return to baseline, if the adverse event was not treatment-related, subsequent treatment with Carfilzomib may resume at full dose. If the event was treatment-related, subsequent treatment with Carfilzomib will resume at one level dose reduction except for nausea, vomiting or diarrhoea which can be attributed to Carfilzomib (see table 5 below). If toxicity continues or recurs, a 2nd Carfilzomib dose reduction may be permitted at the discretion of the investigator. No more than three dose reductions will be permitted in an individual participant on study. If toxicity continues or recurs after three dose reductions, the participant should be discontinued from treatment.

Dose reduction guide for Carfilzomib:

Table 4: Dose Reduction Guide for Carfilzomib Dosing

Current dose	Reduce to
27mg/m ²	20mg/m ²
36 mg/m ²	27 mg/m ²
45 mg/m ²	36 mg/m ²
56 mg/m ²	45 mg/m ²

If the participant tolerates the reduced dose for two cycles, participant may be dose escalated to the dose prior to reduction following discussion with the CI and CTRU.

Dose adjustment guidelines for non-haematologic toxicities are summarised as follows:

Table 5: Dose Adjustment Guidelines for Non-Haematological Toxicities.

Symptom	Recommended Action Carfilzomib
Allergic reaction/hypersensitivity Grade 2 – 3 Grade 4	Withhold until \leq Grade 1, reinstitute at full dose. Discontinue (refer to section 14)
Tumour lysis syndrome (≥ 3 of following: $\geq 50\%$ increase in creatinine, uric acid, or phosphate; $\geq 30\%$ increase in potassium; $\geq 20\%$ decrease in calcium; or ≥ 2 -fold increase in LDH)	Withhold Carfilzomib until all abnormalities in serum chemistries have resolved. Reinstitute at full doses.

Infection Grade 3 or 4	Withhold Carfilzomib until systemic treatment for infection complete and infection resolves. If no neutropenia, restart at same dose. If neutropenic, follow neutropenia instructions.
Herpes zoster of any grade	Withhold Carfilzomib until lesions are dry. Reinstigate at full dose
Grade 3 Nausea or vomiting despite maximal anti-emetic therapy or diarrhoea	Withhold Carfilzomib until this resolves and re-start at full dose. If recurrent, re-start at one dose level lower

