^b Including haematology, biochemistry, paraprotein and immunoglobulins (see Appendix 6 for details)

^c Only if clinically indicated

^d Send to UK NAC as per standard practice. Results will be used to assess haematological response and relapse.

^e visit must be within 28 days of registration

^f Patient must receive 1st cycle of treatment within 6 weeks of reconfirmation of eligibility at the RHC (see 11.1.2).

^g Repeat echocardiogram at end of cycle 2 only (echocardiograms at baseline, prior to cycle 4 and end of treatment will be done at NAC). Echocardiogram to be repeated at any cycle if clinically indicated for unexpected worsening of cardiac function.

^h To be supervised and performed on the day of prescription or in the 3 days prior to the visit to the prescriber.

ⁱ To be supervised and performed four weeks after the end of treatment during the follow-up visit

^j FBC and creatine levels to be checked at day 8 and day 15 (see appendix 6 for details)

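### Protocol section 10.10: the restart condition after an LVEF-drop hold is misprinted, and the scale of the 20% and 15% changes is not stated

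*Protocol*

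**What the plan says.** Protocol section 10.10 has two numeric triggers for holding carfilzomib. One is resting LVEF below 40%. The other is "reduction of LVEF to <55% if the drop is greater than 20% from baseline". The drug may restart when LVEF is back above 40% or, in the words printed for the second kind of hold, "if held due to a drop, < 55% within 15% of baseline". Restart is one dose level lower.

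No other text supplies the missing detail:
- The heart-failure row of Table 5 (section 10.5) points back: "See section 10.10. Any participant with marked worsening of symptoms of congestive heart failure". It then gives a symptom rule with no LVEF value.
- Appendix 4 uses percentage changes in ejection fraction for cardiac response and progression, also without saying whether they are relative changes or points.
- The SAP has no LVEF rule.

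On timing, section 11.2 and Appendix 6 place one echocardiogram at the end of cycle 2, done at the regional haematology centre. Footnote g in section 11.0 adds: "echocardiograms at baseline, prior to cycle 4 and end of treatment will be done at NAC". Others are done when clinically indicated. Section 8.1.1 limits treatment: "A maximum of 6 cycles will be administered".

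**The concern.** A restart rule should describe recovery. This one, as printed, asks a patient held for falling below 55% to be below 55% in order to restart, so the better the recovery, the less likely the patient is to qualify.

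Separately, a 20% fall from a baseline that is itself a percentage can mean a fall to 0.80 of baseline or a fall of 20 ejection-fraction points. The same question applies to the 15% recovery margin. The two meanings can give opposite instructions for the same echocardiogram.

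This is the only numeric LVEF hold and restart rule in the protocol, and section 9.3.3 names section 10.10 as the place where cardiac toxicity management is set out. The regional centres that give the doses also perform the end-of-cycle-2 echocardiogram, with up to four cycles still to come. At stake are dosing at a reduced LVEF, unnecessary loss of treatment after recovery, and different handling of similar patients across the 15 planned centres.

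**Working it through.** The plan states no derived figure to reproduce, so the check applies the section 10.10 rule to a range of baselines. **Inputs from the protocol:** hold below 40%; hold below 55% with a drop of more than 20%; restart above 40%, or within 15% of baseline after a drop hold (section 10.10); entry allowed from an ejection fraction of 40% (section 6.3.2). **Assumption:** the baselines are illustrations, because the documents give no LVEF distribution. B is baseline LVEF in percent.

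**1. Literal restart window after a drop hold.** LVEF must be below 55% and within 15% of B. The lower limit is 0.85B (relative) or B − 15 (points). The window is empty when that limit reaches 55:
- Relative: 0.85B ≥ 55, so B ≥ 55/0.85 = 64.7%.
- Points: B − 15 ≥ 55, so B ≥ 70%.

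| B | Relative: 0.85B | Literal window | Points: B − 15 | Literal window |
|---|---|---|---|---|
| 62 | 52.7 | 52.7 to <55 | 47 | 47 to <55 |
| 65 | 55.25 | none | 50 | 50 to <55 |
| 70 | 59.5 | none | 55 | none |

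A patient with B = 62 who recovers to 58 is 4 points, or 4/62 = 6.5%, below baseline. That is well within 15% on either scale, but fails the printed condition because 58 is not below 55.

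**2. Effect of the scale on the hold itself.** Combining both triggers, carfilzomib is held below max(40, min(55, 0.80B)) on the relative scale and below max(40, min(55, B − 20)) on points.

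| B | Hold below, relative | Hold below, points | LVEF values where the scales disagree |
|---|---|---|---|
| 50 | 40 | 40 | none |
| 55 | 44 | 40 | 40 to <44 |
| 60 | 48 | 40 | 40 to <48 |
| 65 | 52 | 45 | 45 to <52 |
| 70 | 55 | 50 | 50 to <55 |
| 75 | 55 | 55 | none |

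Example: B = 60, LVEF 45. The drop is 15 points, or 15/60 = 25%. The relative reading holds the drug and the points reading continues it.

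**3. Which scale is more cautious.** 0.80B − (B − 20) = 20 − 0.20B, and 0.85B − (B − 15) = 15 − 0.15B. Both are zero or positive for B ≤ 100, so the relative limits are never below the points limits. They do not always require a higher LVEF to restart. When 0.85B ≤ 40, that is B ≤ 47.1%, the above-40% condition governs restart on both scales.

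**4. Where the drop trigger adds nothing to the below-40% trigger.** On points, when B − 20 ≤ 40, so B ≤ 60%. On the relative scale, when 0.80B ≤ 40, so B ≤ 50%.

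**The case against.** The strongest reply is that the misprint can be repaired from its own sentence. The trigger speaks of a reduction to below 55%, so the restart clause was almost certainly meant to say: if held due to a drop to below 55%, until within 15% of baseline. A word lost when the PDF was converted to text cannot be excluded either. The literal reading also errs towards withholding the drug. All of this stands, and the empty windows above describe the printed text and do not predict what sites would do. It does not supply the scale, which no single lost word would explain.

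Exposure is narrow. Only the end-of-cycle-2 and pre-cycle-4 echocardiograms, and any clinically indicated one, can trigger the rule. The pre-cycle-4 one is done at the single national centre, and at end of treatment after six cycles no dose remains. There are backstops. Section 10.5 says "Carfilzomib should be withheld for events" of Grade 3 or above. Section 10.10 requires a hold for marked worsening of heart-failure symptoms and discontinuation if they do not resolve in 2 weeks. Section 10.2 says that if the "AE has not resolved within 14 days the patient must discontinue from therapy". These limit harm, but none gives an LVEF restart value.

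Two stronger readings are tempting:
- **Both triggers met.** A reader might infer a large conflict. At B = 75 and LVEF 38, restart could be just above 40, or at 75 − 15 = 60 or 0.85 × 75 = 63.75, a gap of 20 to 24 points. That example is extreme. At B = 62 and LVEF 38 the limits are 47 or 52.7, a gap of 7 to 12.7 points. A patient who meets both triggers was also held due to a drop, so the drop clause is the natural one to govern. The printed or leaves some doubt, which is easily removed.
- **Table 5.** A reader might take the row "Other non-haematologic toxicity assessed as Carfilzomib-related" as a competing restart rule. It is not one, because heart failure and other cardiopulmonary disorders have their own row, which refers to section 10.10.

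**Conclusion.** The point holds as a wording error in an operative safety rule plus an undefined scale. Read literally, recovery to 55% or more bars restart, and no restart value exists from a baseline of about 64.7% (relative) or 70% (points). Even on the intended reading, the missing scale changes the hold decision over bands of 4 to 8 LVEF points at the illustrated baselines of 55% to 70%. Both gaps should be corrected.

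The consequence is for dosing safety and consistency between sites. The number of patients affected is unknown and could be zero.

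A reader might infer that the MTD or RD is compromised. The documents do not support that. The DLT criteria in section 8.1.4 contain no LVEF threshold, and the DLT window closes at the first cycle 2 dose, before the first scheduled on-treatment echocardiogram. A clinically indicated echocardiogram in cycle 1 could contribute to a treatment delay, and a long delay for toxicity is a DLT criterion. But the Safety Review Committee reviews each DLT, and nothing in the documents indicates that this route would alter the dose decision. No sample size or other stated statistical figure changes.

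**What to change.** Replace the restart sentence in section 10.10 with wording to this effect:

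> *Withhold until LVEF is > 40% and, if held due to a drop to < 55%, is also within 15% of baseline; then resume one dose level lower.*

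The *and* settles the case where both triggers are met, so no extra sentence is needed.

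In the same section, state whether 20% and 15% are relative changes or ejection-fraction points, as confirmed by the clinical team. For that choice, the relative scale is never less cautious than points. On points, the drop trigger does no work at baselines of 60% or below.

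The cost is a short wording amendment. Under section 21.4 it needs the appropriate approvals and distribution to sites. It requires no new assessments.
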